8.1.11 Muscle weakness of triceps and quadriceps

Muscle weakness is one of the typical clinical presentations of late onset GM2-gangliosidosis. Natural history data shows that psoas was the first and most affected muscle in the lower limbs, the quadriceps was also commonly involved. The triceps and interosseous were predominantly involved in the upper limbs (28). Psoas and interosseous weakness will be evaluated in FARS-Neuro. The muscle weakness of triceps and quadriceps will be assessed and considered a sensitivity analysis of the FARS-Neuro.

8.1.12 Regional or national emergency

Attempts should be made to perform all assessments in accordance with the approved protocol to the extent possible. In case this is not possible due to a temporary disruption caused by

an emergency, focus should be given to assessments necessary to ensure the safety of participants and those important to preserving the main scientific value of the study.

Procedures to be considered in the event of a regional or national emergency declared by a governmental agency:

- If onsite visits are not possible, remote visits (eg, with home nurses, home health vendor, etc) may be planned for the collection of possible safety and/or efficacy data.
- If onsite visits are not possible visit windows may be extended for assessment of safety and/or efficacy data that cannot be obtained remotely.
- Use of local clinic or laboratory locations may be allowed.

Contingencies implemented due to emergency will be documented in eCRF.

For a regional or national emergency declared by a governmental agency that results in travel restrictions, confinement, or restricted site access, contingency measures are included in [Section 10.11](#) (Appendix 11).

8.2 SAFETY ASSESSMENTS

Planned time points for all safety assessments are provided in the SoA ([Section 1.3](#)).

8.2.1 Physical examinations

- A complete/full physical examination will include, at a minimum, assessments of the general appearance, examination of the skin; head, eyes (including visual acuity), ears, nose, and throat; lymph nodes; heart, lungs, and abdomen; extremities and joints; and neurological and mental status. Height and weight will also be measured and recorded.
- An abbreviated/brief physical examination will include, at a minimum, general assessments.
- Investigators should pay special attention to clinical signs related to previous serious illnesses.
- Any new finding or worsening of previous finding should be reported as a new AE.

8.2.2 Neurological examination

- Each neurological examination will include, but not be limited to, assessments of the patient's mental status, cranial nerves, motor system (including muscle atrophy, tone and power), deep tendon reflex, sensory, and cerebellar function. The examination should be performed by the same neurologist throughout the study, if possible. When neurological and ophthalmological examinations are performed on the same day, the neurological examination should be performed before the ophthalmological examination.

8.2.3 Vital signs

- Body temperature, heart rate, respiratory rate, and blood pressure will be assessed.

- Blood pressure and pulse measurements will be assessed with a completely automated device. Manual techniques will be used only if an automated device is not available.
- Blood pressure and pulse measurements should be preceded by at least 5 minutes of rest for the participant in a quiet setting without distractions (eg, television, cell phones).
- Vital signs (to be taken before blood collection for laboratory tests) will consist of 1 pulse and 3 blood pressure measurements (3 consecutive blood pressure readings will be recorded at intervals of at least 1 minute). The average of the 3 blood pressure readings will be recorded on the eCRF.
- Ideally, pulse and blood pressure should be obtained and recorded while the participant is in the supine position as well as in the standing position. If the participant is unable to stand, blood pressure may be taken while the participant is sitting with feet dangling. If the participant is unable to stand or sit, pulse and blood pressure may be taken in supine position only.

8.2.4 Electrocardiograms

- 12-lead ECG will be obtained as outlined in the SoA (see [Section 1.3](#)) using an ECG machine that automatically calculates the heart rate and measures PR, QRS, QT, and corrected QT (QTc) intervals.
- For Day 1/Week 1, triplicate ECG (3 ECGs) will be recorded within 5 minutes with at least 1 minute between 2 replicates prior to IMP administration.
- The ECG will be read centrally.

8.2.5 Ophthalmological examination

The effect of venglustat on the lens will be closely monitored throughout the whole study for all participants. The full ophthalmological examination will include slit-lamp examination, funduscopy with pupil dilation and examination of the cornea, lens, and retina.

The evaluation of the lens by photography according to the Age-Related Eye Disease Study (AREDS) Clinical Lens Grading System (ARLNS) will be performed during screening, Week 104, Week 208, early withdrawal or treatment discontinuation, or any time deemed medically necessary.

A conventional confrontation visual field examination such as the Donders' test can be performed by the local ophthalmologist as needed as a part of the eye examination. Systematic visual field test by perimetry is not required for this trial.

A full ophthalmological examination, photography, and ARLNS will be performed during screening (this will serve as a baseline assessment), at Week 104 and at Week 208, or at early withdrawal or treatment discontinuation for all participants.

A full ophthalmological examination will be performed at Week 26, Week 52, and Week 78 for all participants and also at Week 130, Week 156, and Week 182 for participants aged ≥ 2 and < 18 years.

Full ophthalmological examination can be performed at any time if deemed medically necessary.

If a lens abnormality is found, the ophthalmologist at the site should perform pupil dilation, photography, and ARLNS evaluation.

The full ophthalmological examination should be performed by the same ophthalmologist throughout the study, if possible. Abnormal findings reported by the clinical sites will be reviewed by the DMC and/or the clinical site to adjudicate these findings as an adverse event of special interest (AESI) and assess their seriousness/severity.

When neurological and ophthalmological examinations are performed on the same day, the neurological examination should be performed before the ophthalmological examination.

8.2.6 Clinical safety laboratory assessments

- See Appendix 2 ([Section 10.2](#)) for the list of clinical laboratory tests to be performed and to the SoA ([Section 1.3](#)) for the timing and frequency.
- The Investigator must review the laboratory report, document this review, and record any clinically relevant changes occurring during the study in the AE section of the eCRF. The laboratory reports must be filed with the source documents. Clinically significant abnormal laboratory findings are those which are not associated with the underlying disease, unless judged by the Investigator to be more severe than expected for the participant's condition.
- All laboratory tests with values considered clinically significantly abnormal during participation in the study or within 5 half-lives after the last dose of study intervention should be repeated until the values return to normal or baseline or are no longer considered clinically significant by the Investigator or Medical Monitor.
 - If such values do not return to normal/baseline within a period of time judged reasonable by the Investigator, the etiology should be identified and the Sponsor notified.
- All protocol-required laboratory assessments, as defined in Appendix 2 ([Section 10.2](#)), must be conducted in accordance with the laboratory manual and the SoA.
 - If laboratory values from nonprotocol-specified laboratory assessments performed at the institution's local laboratory require a change in participant management or are considered clinically significant by the Investigator (eg, SAE or AE or dose modification), then the results must be recorded in the eCRF.

8.2.7 [REDACTED]

[REDACTED]

[REDACTED]

[REDACTED]

[REDACTED]

8.2.7.1 [REDACTED]

[REDACTED]

[REDACTED]

[REDACTED]

[REDACTED]

8.3 ADVERSE EVENTS AND SERIOUS ADVERSE EVENTS

Adverse event of special interest

An AESI is an AE (serious or nonserious) of scientific and medical concern specific to the Sponsor's product or program, for which ongoing monitoring and immediate notification by the Investigator to the Sponsor is required. Such events may require further investigation in order to characterize and understand them. Adverse events of special interest may be added, modified or removed during a study by protocol amendment.

- Pregnancy of a female participant entered in a study as well as pregnancy occurring in a female partner of a male participant entered in a study with IMP;

- Pregnancy occurring in a female participant entered in the clinical trial or in a female partner of a male participant entered in the clinical trial. It will be qualified as an SAE only if it fulfills one of the seriousness criteria (see Appendix 3 [Section 10.3]).
- In the event of pregnancy in a female participant, IMP should be discontinued.
- Follow-up of the pregnancy in a female participant or in a female partner of a male participant is mandatory until the outcome has been determined (see Appendix 4 [Section 10.4]).
- Symptomatic overdose (serious or nonserious) with IMP;
 - An overdose (accidental or intentional) with the IMP is an event suspected by the Investigator or spontaneously notified by the participant (not based on systematic pills count) and defined as at least twice the intended dose within the intended therapeutic interval, adjusted according to the tested drug.
- Increase in ALT (see the “Increase in ALT” flow diagram in Appendix 6 [Section 10.6]).
- **Other project specific AESI(s)**
 - New or worsening lens opacities and cataracts.

The definitions of an AE or SAE can be found in Appendix 3 (Section 10.3).

Adverse events will be reported by the participant (or, when appropriate, by a caregiver, surrogate, or the participant's legally authorized representative).

The Investigator and any qualified designees are responsible for detecting, documenting, and recording events that meet the definition of an AE or SAE and remain responsible for following up AEs that are serious, considered related to the study intervention or study procedures, or that caused the participant to discontinue the study intervention and/or study (see Section 7).

8.3.1 Time period and frequency for collecting AE and SAE information

All AEs, AESIs, and SAEs will be collected from the signing of the ICF until the 6-week follow-up visit at the time points specified in the SoA (Section 1.3).

All SAEs and AESI will be recorded and reported to the Sponsor or designee immediately and under no circumstance should this exceed 24 hours, as indicated in Appendix 3 (Section 10.3). The Investigator will submit any updated SAE data to the Sponsor within 24 hours of it being available.

Investigators are not obligated to actively seek AE or SAE after conclusion of the study participation. However, if the Investigator learns of any SAE, including a death, at any time after a participant has been discharged from the study, and he/she considers the event to be reasonably related to the study intervention or study participation, the Investigator must promptly notify the Sponsor.

8.3.2 Method of detecting AEs and SAEs

The method of recording, evaluating, and assessing causality of AE and SAE and the procedures for completing and transmitting SAE reports are provided in Appendix 3 ([Section 10.3](#)).

Care will be taken not to introduce bias when detecting AEs and/or SAEs. Open-ended and nonleading verbal questioning of the participant is the preferred method to inquire about AE occurrences.

8.3.3 Follow-up of AEs and SAEs

After the initial AE/AESI/SAE report, the Investigator is required to proactively follow each participant at subsequent visits/contacts. At the prespecified study end-date, all SAEs, and nonserious AESI (as defined in [Section 8.3](#)) will be followed until resolution, stabilization, the event is otherwise explained, or the participant is lost to follow-up (as defined in [Section 7.3](#)). Further information on follow-up procedures is given in Appendix 3 ([Section 10.3](#)).

8.3.4 Regulatory reporting requirements for SAEs

- Prompt notification by the Investigator to the Sponsor of an SAE is essential so that legal obligations and ethical responsibilities towards the safety of participants and the safety of a study intervention under clinical investigation are met.
- The Sponsor has a legal responsibility to notify both the local regulatory authority and other regulatory agencies about the safety of a study intervention under clinical investigation. The Sponsor will comply with country-specific regulatory requirements relating to safety reporting to the regulatory authority, Institutional Review Boards (IRB)/Independent Ethics Committees (IEC), and Investigators.
- Investigator safety reports must be prepared for suspected unexpected serious adverse reactions (SUSAR) according to local regulatory requirements and Sponsor policy and forwarded to Investigators as necessary.
- Adverse events that are considered expected will be specified in the reference safety information.
- An Investigator who receives an Investigator safety report describing an SAE or other specific safety information (eg, summary or listing of SAEs) from the Sponsor will review and then file it along with the Investigator's Brochure and will notify the IRB/IEC, if appropriate according to local requirements.

8.3.5 Pregnancy

- Details of all pregnancies in female participants and female partners of male participants will be collected after the start of study intervention and until the 6-week follow-up visit.
- If a pregnancy is reported, the Investigator should inform the Sponsor within 24 hours of learning of the pregnancy and should follow the procedures outlined in Appendix 4 ([Section 10.4](#)).

- Abnormal pregnancy outcomes (eg, spontaneous abortion, fetal death, stillbirth, congenital anomalies, ectopic pregnancy) are considered SAEs.

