Based on the available clinical data the risk of depression was assessed as a potential risk for GBA-PD population. The limited available data doesn't allow		

 

 

Description	Summary of data/rationale	Mitigation strategy
to confirm this risk for other venglustat indications.		

Syncopal
 
Based on the available clinical data the risk of syncope was assessed as a potential risk for GBA-PD population. The limited available data doesn't allow to confirm this risk for other venglustat indications
	
Clinical findings specific for GBA-PD population suggesting more frequent events of syncope in venglustat arm compared to placebo arm.
	
Neurological examinations and adverse events monitoring.

Transient increase in BP at the beginning of venglustat treatment
	
Transient BP increase in venglustat-treated participants of approximately 5 mmHg, within the first 6 months of treatment. See IB Section 7.1.
	
BP monitoring at site visits and at home. See SOA (Section 1.3) and Section 8.3 of the protocol.

Embryo-fetal toxicity (important potential risk)
	
In the embryo-fetal toxicology studies in rats and rabbits, increased implantation loss (in rats) and reduced fetal weight (in both rats and rabbits) were observed. See IB, Section 7.2.1.3.
	
Men and women of childbearing potential (premenopausal and not surgically sterile) are required to either practice true abstinence consistent with their preferred and usual lifestyle, or use double contraceptive methods, including a highly effective method (see Section 5.1 and Section 10.4 for details) for the entire duration of the study and for at least 6 weeks for females and at least 90 days for males following their last dose of IMP.

Drug interactions
		

Abbreviations: [redacted] IB=Investigator's Brochure; IMP=Investigational Medicinal Product.

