Female patients of childbearing potential and sexually active male patients must be willing to practice true abstinence in line with their preferred and usual lifestyle, or use 2 acceptable effective methods of contraception for the duration of the study and for at least 6 weeks for females and 90 days for males following their last dose of IMP. In addition, male participants must refrain from donating sperm for the duration of the study and for 90 days after the last dose of IMP.

a) Sexually active male participants

A male participant must agree to use contraception as detailed in Appendix 4 (Section 10.4) of this protocol for the duration of the study and 90 days following their last dose of IMP.

b) Female participants

A female participant is eligible to participate if she is not pregnant (see Appendix 4 [Section 10.4]), not breastfeeding, and at least one of the following conditions applies:

- Not a woman of childbearing potential (WOCBP) as defined in Appendix 4 (Section 10.4)

OR

- A WOCBP who agrees to follow the contraceptive guidance in Appendix 4 (Section 10.4) for the duration of the study and for at least 6 weeks after the last dose of IMP.

Informed Consent

I 08. The participant or, if appropriate, parent(s) or legal guardian(s) must provide written informed assent/consent prior to any study-related procedures being performed as described in Appendix 1 (Section 10.1). Note: For criteria specific to participants enrolled in Japan and France, see Appendix 8 (Section 10.8).

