- Hormonal contraception may be susceptible to interaction with the study intervention, which may reduce the efficacy of the contraceptive method. In this case, 2 highly effective methods of contraception should be utilized during the intervention period and for at least 6 weeks after the last dose of study intervention.

PREGNANCY TESTING:

- WOCBP should only be included after a negative serum pregnancy test.
- Additional pregnancy testing should be performed at monthly intervals during the intervention period and as required locally.
- Pregnancy testing will be performed whenever a menstrual cycle is missed or when pregnancy is otherwise suspected.

COLLECTION OF PREGNANCY INFORMATION:

Male participants with partners who become pregnant

- The Investigator will attempt to collect pregnancy information on any male participant's female partner who becomes pregnant while the male participant is in this study. This applies only to male participants who receive study intervention.
- After obtaining the necessary signed informed consent from the pregnant female partner directly, the Investigator will record pregnancy information on the appropriate form and submit it to the Sponsor within 24 hours of learning of the partner's pregnancy. The female partner will also be followed to determine the outcome of the pregnancy. The Investigator will collect follow-up information on the neonate (Note: follow-up to 1 year after birth) and the information will be forwarded to the Sponsor. Information on the status of the mother and child will be forwarded to the Sponsor. Generally, the follow-up will be no longer than 6 to 8 weeks following the estimated delivery date. Any termination of the pregnancy will be reported regardless of fetal status (presence or absence of anomalies) or indication for the procedure.

Female participants who become pregnant

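### Minor: the protocol makes pregnancy in a male participant's female partner an AESI, but SAP Table 11, which sets AESI selection, names only pregnancy in female subjects

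*Protocol*

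**What the plan says.** **AESI definition.** Protocol Section 8.3 lists as AESIs pregnancy in a female participant or in a male participant's female partner, symptomatic overdose, ALT increase, and new or worsening lens opacities and cataracts. It adds that the list is changed by protocol amendment.

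**Collection.** Section 8.3.5 covers pregnancies in female participants and female partners, whose details "will be collected after the start of study intervention and until the 6-week follow-up visit". It also says that "the Investigator should inform the Sponsor within 24 hours of learning of the pregnancy". Appendix 4 (Section 10.4) has the investigator try to collect information on any "female partner who becomes pregnant while the male participant is in this study". The newborn is followed too ("Note: follow-up to 1 year after birth"). Section 8.3.1 sets the general window: "All AEs, AESIs, and SAEs will be collected from the signing of the ICF until the 6-week follow-up visit".

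**Analysis.** SAP 3.6.2 has AESIs and other events of interest selected according to Table 11. That table has four rows: pregnancy in a female subject, symptomatic overdose, ALT increase, and lens opacities and cataracts. The pregnancy row selects from a tick box on the AE page or a dedicated eCRF page. Table 10 tabulates treatment-emergent AESIs by system organ class and preferred term. Post-treatment AEs get only an overview, whose footnote lists any AE, serious AEs, AEs leading to death and AEs leading to permanent discontinuation.

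**Contraception.** Table 2, under Section 2.3.1.6, requires it "for at least 6 weeks for females and at least 90 days for males following their last dose of IMP". Section 5.1 (I 07) sets the same periods.

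**The concern.** Table 11 is the SAP's rule for what counts as an AESI in the safety tables. A programmer who follows it would build a pregnancy category for female subjects and have no instruction to include partner pregnancies. An event that the protocol singles out for immediate notification could then be missing from the AESI output, or present under a label that does not describe it.

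This matters a little more than an ordinary label. Section 2.3.1.6 calls embryo-fetal toxicity an important potential risk and states that venglustat has not been studied in pregnant women. Each recorded pregnancy is therefore informative, including one with a normal outcome.

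**Working it through.** No power, alpha or sample-size figure is involved. The main check sets the texts side by side; the arithmetic serves only the related timing question.

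**1. AESI lists compared.**

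| Protocol 8.3 | SAP Table 11 |
|---|---|
| Pregnancy, female participant | Named |
| Pregnancy, partner of a male participant | Not named |
| Symptomatic overdose | Named |
| ALT increase | Named |
| Lens opacities and cataracts | Named |

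One of the two pregnancy categories is missing; everything else carries over.

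**2. Was the category removed on purpose?** Removal would take a protocol amendment. The visible summaries of changes for Amendments 01 to 06 show none, nor do SAP Table 1 or SAP 3.9 (Table 12). Some amendment rows are redacted, but the current Section 8.3 still contains the category.

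**3. Where a recorded partner pregnancy would appear.**
- *Within the treatment-emergent period* (SAP 3.1: to last dose plus 6 weeks, or to the end of the primary analysis period if that comes first). If entered as an AE, it can appear in the general AE tables under its preferred term. Table 11 gives it no category.
- *Afterwards, while the man is still in the study.* It can add to the post-treatment AE overview, which has no AESI category. This can occur because Section 7.1.1 keeps participants in the study after they stop drug. As an illustration, a man who stops at Week 52 and stays to Week 104 has 104 − (52 + 6) = 46 weeks of post-treatment time, within the Appendix 4 collection wording.

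**4. Collection against contraception for men.** Inputs: 90 days of contraception (Section 5.1, Table 2) and a follow-up visit 6 weeks after treatment, ±7 days (Section 1.3). The last dose is taken to fall at the end-of-treatment visit.
- Nominal: 90 − 42 = 48 days (48/90 = 53%).
- Visit at day 49: 90 − 49 = 41 days (46%).
- Visit at day 35: 90 − 35 = 55 days (61%).
- Appendix 11 allows the window for Visits 3 to 12 to be extended by up to 3 months in a declared emergency. Visit 12 is the follow-up visit, so the gap can then shorten or close.
- Women: 42 − 42 = 0 days.

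**5. Likely yield of closing that gap.** The documents do not give the number of sexually active men, so it is assumed. Expected pregnancies = men × 48/365 × annual rate.
- 29 men (about half of 57): 29 × 48/365 = 3.81 person-years. That gives 0.04 at the 1% per year ceiling that Appendix 4 sets for the partner's method, and 0.4 at an assumed 10%.
- 77 men (57 + 20, a bound that cannot be reached): 10.13 person-years, giving 0.10 and 1.0.
- Drug remaining at day 42: 42 × 24 / 31.3 = 32 half-lives, using the healthy-volunteer value in Section 2.2.2.

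**The case against.** **It is only a label.** Selection runs through a tick box or dedicated eCRF page, which may already hold partner pregnancies, and preferred-term coding may give them their own line in Table 10. This stands in part. The eCRF and coding are not visible, so one cannot say that the data are lost or that the events would be invisible. It does not repair the rule, however: the SAP states what is to be selected, and partner pregnancy is not in the statement.

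**A stronger reading.** A reader might infer that the protocol itself is wrong, because men must use contraception for 90 days while active collection stops at about 6 weeks. After that, "Investigators are not obligated to actively seek AE or SAE after conclusion of the study participation". The documents do not support calling this an error, for four reasons:
- Contraception is prevention and Section 8.3.5 is a collection window. No text says that they must be equal, and Sections 8.3.1 and 8.3.5 and Appendix 4 broadly agree on stopping at the 6-week visit or with study participation.
- Passive routes remain. The sponsor is told of a pregnancy the investigator learns of (though this may be read as limited to the collection window). Abnormal outcomes are SAEs, and SAEs considered related are reportable after discharge. A known pregnancy is followed to its outcome.
- The visible text states no male-mediated fetal risk, and some 32 half-lives have passed by day 42.
- The gap does not apply to women, or to men who stop drug but stay in the study past day 90.

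What is lost is mainly active enquiry, chiefly about pregnancies with a normal outcome or judged unrelated.

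**Conclusion.** The SAP is wrong as written on one small point. It omits one of the protocol's two pregnancy categories from AESI selection, and the post-treatment overview has no AESI category to pick it up. This rests on Section 8.3 and Table 11 as they now stand, and on no redacted entry having removed the category. The number of events affected cannot be estimated, since the documents give neither the number of sexually active men nor the eCRF layout.

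The 48-day difference (41 to 55 with the visit window, shorter under the emergency extension) is a design choice. Extra contact would probably find fewer than one pregnancy, given the assumed numbers of men and rates.

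**What to change.** **Change to make.** Reword the Table 11 pregnancy row so that it covers pregnancy in a female participant and pregnancy in the female partner of a male participant, selected from the same tick box or eCRF page. Add to SAP 3.6.2 that all recorded pregnancies are listed, whether they fall in the treatment-emergent or post-treatment period. The cost is one table row, one sentence and one listing. It is confined to the SAP, adds no procedure for participants, and leaves efficacy analyses, alpha, power and dosing alone.

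**Optional.** At the next amendment the sponsor could consider one telephone contact at about day 90 for sexually active men who have left the study. This costs more than the call. It needs edits to Sections 8.3.1 and 8.3.5, Appendix 4 and the telephone row of the Schedule of Activities, with IRB/IEC approval and re-consent. The SAP 3.1 observation periods and the end-of-study definition (Section 4.4) would also need attention, or the data would fall outside them. Section 9.5 and SAP 3.8.2 should say that the call does not delay the second-step analysis. A day-90 call would also miss conceptions in the last weeks before it. On the expected yield, leaving this out is reasonable.
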